10.7 Interim analysis

Not applicable.

10.8 Data monitoring committee

Not applicable.

10.9 Withdrawals and deviations

All withdrawn subjects will be listed individually, including at least subject number, date and reason for withdrawal, and last visit performed.

Subjects with protocol deviations will be listed individually, including subject number and observed deviation. Depending on the seriousness of the deviation, subject might be excluded from the PP population, which should be documented prior to database lock.

Deviations from the statistical plan will be documented CSR.

10.10 Sample size

11. Protection of personal data

All processing of personal data must be carried out in accordance with national legislation concerning the protection of personal data. The Institution and the Investigator are responsible for complying with all requirements pursuant to national legislation in which the Institution and the Investigator are located. The Sponsor will ensure that all requirements for data processing are fulfilled.

The Investigator understands that clinical studies conducted under an IDE are exempt from the study subject identifier confidentiality provisions of the Health Insurance Portability and Accountability Act of 1996 (HIPAA), and the study subject should be made aware of this exception in the informed consent. The Institution and Investigator are jointly responsible for providing sufficient information to all subjects to enable them to give their informed consent not only to the participation in the investigation, but also to the processing of Personal Data. Such information includes information regarding the purposes of the processing, the length of time during which Personal Data will be stored, the right of access to stored Personal Data and the right to correction or purging of incorrect or obsolete Personal Data. A subject may also withdraw his or her consent at any time.

A subject who withdraws his or her consent to the processing of Personal Data must be considered to have withdrawn from the investigation but the data collected until the consent was withdrawn may be used in the statistical analyses.

Authorized representatives from the Sponsor or a RA may visit the investigational site to perform audits/inspections, including source data verification, i.e., comparing data in the subjects' medical records and the eCRF. Data and information will be handled with strict confidentiality.

12. Quality Control and Quality Assurance

12.1 Quality control

On-site monitoring of the study will be arranged by the Sponsor according to GCP guidelines to verify that the rights and well-being of the subjects are protected, the reported data are accurate, complete, verifiable from source documents, and that the conduct of the study complies with the approved CIP, subsequent amendment(s), GCP and the applicable regulatory requirements.

Any CIP deviation shall be reported in the eCRF, which will be verified, discussed, and collected by the monitor and appropriate actions will be taken. The Investigator is responsible for promptly reporting any deviations from the CIP that affects the rights, safety or well-being of the subject or the scientific integrity of the study, including those which occur under emergency circumstances, to the Sponsor as well as the IRB if required by national regulations. Deviations will be reviewed to determine the need to amend the CIP or to terminate the study. Handling of CIP deviations will be performed as described in the monitoring manual.

12.2 Quality assurance

The study site may be subject to quality assurance audit by the Sponsor as well as inspection by appropriate RA. It is important that the Investigator and other relevant study site personnel are available during the monitoring visits, possible audits, and inspections, and that sufficient time is devoted to the monitoring process.

Each participating member of the study site team shall provide a curriculum vitae (CV) or equivalent that demonstrates their qualifications to conduct the study.

It is the responsibility of the Investigator to ensure that all personnel involved in the study are fully informed of all relevant aspects of the study, including detailed knowledge of and training in all procedures to be followed. All Investigators and other responsible persons shall be listed together with their function in the study on a signature and delegation log.

[REDACTED]

[REDACTED]

13. Financing, Indemnification, and Insurance

The CTA outlines the compensation and payment terms of the study. The CTA must be signed before the first subject is screened in the study. If there are differences between the CTA and the CIP regarding certain rights and obligations, the CTA is the prevailing document.

The Sponsor's obligations in this clinical study are covered by Galderma's global general liability program. An insurance certificate will be provided upon request. The Institution/Investigator is obligated to maintain insurance coverage for their obligations in the clinical study according to the CTA.

[REDACTED]

[REDACTED]

[REDACTED]

15. Suspension or Premature Termination

The Sponsor will suspend or terminate the study when so instructed by the IRB or FDA, or if it is judged that the subjects are subjected to unreasonable risks, or for valid scientific or administrative reasons.

The Sponsor may also decide to close a single study site due to unsatisfactory subject enrollment or non-compliance with the CIP, GCP, or applicable regulatory requirements.

In the event of premature termination, the Sponsor will provide information on the handling of currently enrolled subjects who have not completed the study.

¹⁰ Defining the role of authors and contributors, compiled by the International Committee of Medical Journal Editors (ICMJE) (<http://www.icmje.org>).

16. References

N/A

Title

43USV1704 CIP Volyme Midface

Doc id

Title

43USV1704 CIP Volyme Midface

Doc id

Title

43USV1704 CIP Volyme Midface

Doc id

Title

## TABLES

## 1.0 PURPOSE

This SAP describes the methods to be used in the analysis of study data from clinical protocol 43USV1704 titled "A Randomized, Evaluator-Blinded, Parallel, Comparator-Controlled Study to Evaluate the Safety and Effectiveness of GAL1704 for Cheek Augmentation and the Correction of Midface Contour Deficiencies" in order to answer the study objective(s), and is based on version 3.0 of the study protocol, dated 28AUG2018.

Populations for analysis, data handling rules, statistical methods, and formats for data presentation are described within this document. The statistical analyses and summary tabulations described in this SAP will provide the basis for the results sections of the CSR for this study. The SAP outlines any differences in data analysis methods relative to those planned in the study protocol. Any changes to the data analysis methods after database lock will be described in the CSR.

## 2.0 ACRONYMS

Below is the list of acronyms that will be used throughout this document.

Abbreviation	Description
AE	Adverse Event
AESI	Adverse Event of Special Interest
ATC-3	Anatomical Therapeutic Chemical 3th level
BE	Blinded Evaluator
BMI	Body Mass Index
BOCF	Baseline Observation Carried Forward
CDISC	Clinical Data Interchange Standards Consortium
CIPR	Central Independent Photographic Reviewer
CSR	Clinical Study Report
G	Gram
eCRF	Electronic Case Report Form
EOS	End of Study
ET	Early termination
eCTD	Electronic Common Technical Document
FST	Fitzpatrick Skin Type
[REDACTED]	[REDACTED]
ICH	International Conference on Harmonisation
ICF	Informed Consent Form
IP	Investigational Product
IPR	Independent Photographic Reviewer
IRE	Injection Related Events
ISO	International Organization for Standardization
ITT	Intention-to-treat
MedDRA	Medical Dictionary for Regulatory Activities

Abbreviation	Description
[REDACTED]	[REDACTED]
NPS	Numeric Pain Scale
PP	Per Protocol
PT	Preferred Term
SAE	Serious Adverse Event
SAP	Statistical Analysis Plan
SD	Standard Deviation
SOC	System Organ Class
SOP	Standard Operating Procedure
TC	Telephone Call
WHO	World Health Organization
Tx	Treatment

## 3.0 OVERALL STUDY DESIGN AND OBJECTIVE

### 3.1 Study Objectives

#### 3.1.1 Primary Effectiveness Objective

The primary objective of the study is to demonstrate non-inferiority of GAL1704 versus a comparator-control in cheek augmentation by comparing change from baseline in the blinded evaluator (BE) live assessment of midface fullness at 12 weeks after the last injection, [REDACTED]  
[REDACTED].

#### 3.1.2 Secondary Effectiveness Objectives

- [REDACTED]
- [REDACTED]
- [REDACTED]
- [REDACTED]

### 3.1.3 Safety Objectives

The safety objectives of this study are:

- i) To evaluate all adverse events (AEs) collected throughout the study.
- ii) To evaluate pre-defined, injection related events (IREs) reported during the first 4 weeks after each treatment as recorded in the subject diary.
- iii) To evaluate subject pain for each cheek individually – before (prior to application of anesthetic) and immediately following (before any post-injection procedures) each injection session using an [REDACTED] Numeric Pain Scale (NPS).
- iv) To evaluate the following safety assessments, as assessed by a qualified staff member, according to pre-defined methods, at baseline and each subsequent on-site follow up visit:

[REDACTED]

### 3.1.4 Exploratory Objectives

### 3.2 Study Design and Study Procedures

This is a randomized, evaluator-blinded, parallel group, comparator-controlled, multi-center, US study to evaluate the effectiveness of GAL1704 for cheek augmentation and the correction of midface contour deficiencies.

### 3.3 Treatments and Assignment to Treatments

Subjects will be enrolled in two groups – Group A and Group B.

**Group A:** Approximately 210 subjects, over the age of 21, will be randomized in a 2:1 ratio, to receive treatment with either GAL1704 or Juvéderm Voluma® XC, respectively. Approximately 140 subjects will be treated with GAL1704 and 70 subjects will be treated with Juvéderm Voluma® XC.

[REDACTED]  
sites will have a BE, blinded to the treatment provided to each subject, who will perform the blinded assessments.

**Group B:** An additional 60 subjects will be enrolled and treated with GAL1704 only. These subjects will be treated using a split face design, i.e., one cheek will be treated using a small blunt tip cannula and the other cheek will be treated using the co-packed needle.

[REDACTED]  
[REDACTED] The Treating Investigator will not be blinded to study treatments and will administer the treatments to each subject. Safety assessments will be performed by non-blinded personnel.

### 3.4 Determination of Sample Size

For sample size calculation of Group A,

Accounting for approximately 12% drop-outs and non-evaluable subjects due to protocol deviations at Week 12, a total of approximately 210 subjects will be randomized in the study. It is expected that the number of randomized subjects will be similar across the study sites.

For sample size calculation of Group B, [REDACTED]

Accounting for approximately 10% drop-outs, 60 subjects will be needed.

Thus, a total of 270 subjects will be included in the study.

## 4.0 GENERAL ANALYSIS CONVENTION

Data collected in this study will be documented using summary tables and subject data listings. Continuous endpoints will be summarized using descriptive statistics, e.g. number of subjects, mean, median, standard deviation, minimum and maximum values. Categorical endpoints will be presented in frequency tables with number and percentage of observations for each level.

Group A and Group B will be analyzed and presented separately. Data will be summarized by treatment group in Group A and by injection tool (Needle/Cannula) in Group B.

Confidence intervals will be two-sided and constructed at a confidence level of 95%.

Study days will be calculated relative to the date of first dose of study product. Day 1 will be the first day of study product administration in the study. The day prior to Day 1 will be Day -1. There will be no Day 0.

Baseline will be the last assessment prior to the first dose of study product.

#### 4.1 Study Visits

#### 4.2 Visit Windows

Study visits are expected to occur according to the protocol schedule. All data will be tabulated per the evaluation visit as recorded on the eCRF even if the assessment is outside of the visit window. In data listings, the relative study day of all dates will be presented. There will not be any windowing for unscheduled visits in the analysis. Unscheduled visits, if any, will be considered in determination of baseline.

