5.5 Withdrawal of subjects

Each subject shall be advised in the informed consent form that the subject has the right to withdraw from the study at any time, for any reason, without prejudice. Subjects may also be discontinued from this study if the Investigator determines that it is in the subject's best interest to do so, and may be withdrawn at the Investigator's discretion at any time.

[REDACTED]

[REDACTED]

[REDACTED]

[REDACTED]

[REDACTED]

The reason and date for withdrawal should be documented in the subject's source documents and eCRFs. When possible, an explanatory comment should be added to further explain the reason for withdrawal. If withdrawal of a subject occurs during a regular investigational visit, the eCRF for that specific visit should be completed as far as possible.

If withdrawal of a subject occurs between regular study visits the subject should, when possible (irrespective of the reason for withdrawal) be scheduled for an early termination visit to document subject outcome for the primary and secondary endpoints.

If a subject is withdrawn from the study, all data collected until the time of withdrawal will be used in the analyses.

Subjects who receive product and are withdrawn or discontinued from the study will not be replaced.

For AEs still ongoing at the time of the withdrawal, see (Section 8.6.8).

6. Study Products

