10.6 Handling of missing data

Number of missing values will be summarized and reported as appropriate.

Missing data for the primary analysis [REDACTED] will be handled using the hot deck imputation method.

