## 9.0 EFFECTIVENESS VARIABLES

### 9.1 Primary Effectiveness Variable

Change from baseline in the blinded evaluator (BE) live assessment of midface fullness, for the right and left side of the face, at 12 weeks after the last injection, [REDACTED].

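### Does the SAP's visit-label rule discard early-termination scores and put a donor's value in their place at Week 12?

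*SAP*

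**What the plan says.** Protocol 5.5 says that a subject who withdraws between regular visits should, when possible, "be scheduled for an early termination visit to document subject outcome for the primary and secondary endpoints". It adds that "all data collected until the time of withdrawal will be used in the analyses". If the withdrawal happens at a regular visit, "the eCRF for that specific visit should be completed as far as possible", so those data carry that visit's own label.

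SAP 9.1 defines the primary variable by elapsed time, counted from the final injection: "Change from baseline in the blinded evaluator (BE) live assessment of midface fullness, for the right and left side of the face, at 12 weeks".

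SAP 4.2 sets the tabulation rule: "All data will be tabulated per the evaluation visit as recorded on the eCRF even if the assessment is outside of the visit window". On unscheduled visits it says: "There will not be any windowing for unscheduled visits in the analysis". The one use it gives them is in determining baseline.

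Protocol 10.6 says that missing data for the primary analysis "will be handled using the hot deck imputation method", with the words that set its scope redacted. SAP 11.1 adds an observed-case sensitivity analysis in the ITT population and leaves other effectiveness endpoints unimputed. SAP 5.0 requires a completed Week 12 visit for the per-protocol population.

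**The concern.** Taken together, these sentences seem to collect a measurement for the primary endpoint and then give it no use. A blinded-evaluator score taken at an ET visit about 11 weeks after the last injection would keep its ET label. Week 12 would count as missing, and a donor's value would stand in. A visit labelled Week 12 would be accepted however late it took place. The observed-case sensitivity analysis would leave out the same ET scores, so it would not show the effect.

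The fear is directional. Suppose subjects who leave because of a poor result are more common on GAL1704. Replacing their outcomes with those of subjects who stayed would then favour non-inferiority, and also the superiority claim that follows it.

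**Working it through.** **Who could be affected.** SAP 3.4 allows about 12% for drop-outs and non-evaluable subjects at Week 12 in Group A. The SD, power and pre-inflation sample size are not in the visible text, so 210 cannot be derived from first principles, but the stated figures agree with one another:

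- 210 × 0.88 = 184.8 evaluable, and 184 / 0.88 = 209.1, which rounds up to 210.
- A 2:1 split of 210 gives 140 and 70.
- In Group B, 54 / 0.90 = 60, and 210 + 60 = 270.

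The allowance is therefore 210 − 184.8 = 25.2, or about 25 subjects. From these, remove those who are non-evaluable through protocol deviations, those who withdraw at a regular visit, and those who do not attend an ET visit. Subjects who leave after Week 12, in a study lasting up to 74 weeks (Protocol 4.3), keep their observed Week 12 score.

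**What the sentences commit the analysis to.**

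- SAP 4.2 is a visit-label convention that does not name ET visits. Its sentence on windowing concerns unscheduled visits, whereas Protocol 5.5 describes an ET visit as one that is scheduled. How the eCRF labels an ET assessment cannot be seen.
- The endpoint is fixed at 12 weeks after the last injection. A score taken earlier is a different quantity, so a donor value would fill a missing Week 12 score and not overwrite an observed one. Only an ET score inside the Week 12 window could fairly be called Week 12, and the visible text does not give that window.
- The promise in Protocol 5.5 is use in the analyses, not use as the Week 12 value. By-visit summaries, safety analyses or information for the imputation could meet it.

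**Where a rule would sit.** SAP 4.1 is a bare heading, most of 10.1 is redacted, 11.1 has two redacted blocks next to its missing-data text, and the schedules of events are not shown. SAP 18.0, on changes from the protocol, is in the table of contents but not visible. The SAP's acronym list defines both ET and BOCF (baseline observation carried forward), yet the visible SAP uses neither. That suggests hidden text on the subject but does not prove it. If baseline were carried forward, no donor would be involved and the feared direction of bias would not follow.

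**Possible size.** Let f be the share of an arm with only an ET score and d the mean gap between own and donor scores. Then

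net shift = f(GAL1704) × d(GAL1704) − f(comparator) × d(comparator).

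Equal effects in the two arms cancel. Setting the comparator term to zero is the least favourable case when both gaps have the same sign. The values of f and d below are assumptions; the documents give neither.

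| f | d (units) | Shift (units) | Share of 0.5 margin |
|---|---|---|---|
| 2% | 0.25 | 0.005 | 1% |
| 3% | 0.5 | 0.015 | 3% |
| 5% | 0.5 | 0.025 | 5% |
| 8% | 1.0 | 0.08 | 16% |
| 12% | 1.0 | 0.12 | 24% |

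The last row treats the whole allowance as ET cases. Per subject, one GAL1704 subject whose own score is a full unit worse than the donor's moves the arm mean by 1.0 / 140 = 0.007 units, or 1.4% of the margin. Relabelling ET scores as Week 12 would reach only those inside the window, a smaller share than f.

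**The case for a change.** The strongest reply is that SAP 4.2 shows no redaction, covers all data, and refers to the analysis as well as to table layout. A hidden ET rule would be an exception that this section does not announce. Elapsed time defines the endpoint, so the form's name should not decide which scores count. The study day shown in listings runs from the first dose (SAP 4.0), so after an optional touch-up it does not show time since the last injection. Protocol 5.5 names the primary endpoint as the purpose of the ET visit, and a listing alone would be a thin way to honour that. Superiority is judged against 0, where a small shift could matter more than it does against 0.5.

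Part of this stands. No visible passage says whether an ET score can count as Week 12 or inform the hot deck, and on a literal reading the contrast with late Week 12 visits is real.

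The rest carries less weight. Accepting late visits under their nominal label is an ordinary ITT convention, and the per-protocol analysis can exclude deviations with substantial impact (SAP 5.0 and 7.0). An observed-case analysis leaves out subjects without a Week 12 value by definition. Assessment and injection dates allow time since the last injection to be derived. That subjects with poor results leave GAL1704 more often is a supposition without support in the documents.

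**Conclusion.** No change to the plan is called for. The visible text lacks a detail on ET assessments, but it does not contradict itself, and discarding an observed outcome in favour of a donor's is an inference from a rule that never mentions ET visits. Keeping an early score out of Week 12 is defensible. For the few scores that fall at the right time, an analyst has the dates needed to make a sensible assignment. Whether the remaining ET scores help the imputation depends on specifications that are redacted.

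The number affected is at most about 25 of 210 in Group A if losses match the planning allowance, and probably far fewer. The illustrative shift of 0.005 to 0.12 units (1% to 24% of the margin) assumes values of f and d that have no source in the documents, and no offset from the comparator arm. Its direction is unknown. Following the visible plan is not shown to lead to an unsound conclusion. This judgement rests on the public text, since the redacted parts of SAP 4.1, 10.1 and 11.1 may already settle the matter.

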## 5.0 ANALYSIS POPULATIONS

The Analysis Populations are defined separately for Group A and Group B as described below.

- **Safety Population:** Includes all subjects who were injected at least once. Subjects are analysed according to the treatment they actually received.

- **Intention-to-Treat (ITT) Population:** Includes all subjects who were randomized. Subjects are analysed according to the treatment they were randomized to.
- **Per-Protocol (PP) Population:** Includes all subjects in ITT who complete the Week 12 visit without any deviations considered to have substantial impact on the primary effectiveness outcome.

Safety population will be the basis for all safety evaluations. When performing effectiveness analysis, the ITT population will be used. Primary effectiveness analysis will be repeated using the PP populations. Additional endpoints maybe explored in the PP population if deemed necessary.

## 6.0 SUBJECT DISPOSITION

Subject disposition will be summarized separately for Group A and Group B. The number of subjects screened and randomized will be presented. The number of subjects in the Safety, ITT and PP populations will be summarized. The number and percentage of subjects in the ITT population who complete the study will be summarized, along with the number and percentage of subjects who do not complete the study for each discontinuation reason as specified on the eCRFs.

Subject accountability will be summarized by visit with the following:

- i) Number of subjects expected at each visit
- ii) Number of subjects performed each visit
- iii) Number of subjects missed at each visit
- iv) Number of subject withdrawn at each visit

Data will be summarized by treatment group and overall except for the number of subjects screened.

All withdrawn subjects will be listed individually, including at least subject number, date, and reason for withdrawal, and last visit performed.

Inclusion/exclusion data will be presented by subjects in a data listing.

